| Inclusion/Exclusion Criteria | 
Inclusion Criteria:
 
 1. Adults (18 years old and above) 2. Confirmed HIV infection (including both antiretroviral (ART)- naïve and experienced) 3. Being admitted to the hospital 
Exclusion criteria:
 
 1. Unable to provide informed consent (if no authorized relatives are in the position to provide the consent) 2. Living outside the catchment area of the participating hospital(s) 3. With plans to migrate outside the catchment area within 2 months after recruitment. 4. Currently receiving anti-TB therapy or having received anti-TB therapy (or a TB diagnosis) in the last 6 months prior to enrolment 5. Currently receiving or having received preventive TB treatment in the preceding 6 months 6. Patients admitted for traumatic reasons, acute abdomen, delivery or pregnancy (maternal conditions) or for planned/scheduled surgery. 7. Referred from other reference hospital 8. Positive result to a SARS-CoV-2 test (RT-PCR, antigen test, or other similar test that might define COVID-19 case in the study site)* 
*AND patients under investigation for COVID-19 if this situation hinders the execution of study activities (as judged by the site PI)
 |
| Evaluation Criteria | 
Primary Endpoint(s):
 
The proportion of participants diagnosed with microbiologically confirmed TB and started on TB treatment within 72 hours of enrolment* in whom TB is microbiologically confirmed*/**, separately for control and intervention arms.
 |

This project is part of the EDCTP2 programme supported by the European Union

E D C T P

*The numerator of the primary endpoint includes participants per study arm who are diagnosed with microbiologically confirmed TB and initiated TB treatment within 72 hrs of enrolment. The denominator is the number of enrolled patients in each study arm.

**Patients are defined to have microbiologically confirmed TB if at least one confirmatory TB test (Ultra, AlereLAM) gives a positive result.

Secondary endpoints:

- Eight-week all-cause mortality (main secondary endpoint) among all participants enrolled. The numerator will be number of deaths during eight weeks after enrolment, the denominator is the number of participants enrolled.

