10.4 Recruitment

A participant is considered recruited for the study when the participant has signed the informed consent, meets all the inclusion criteria and does not fulfill any of the exclusion criteria.

For those patients enrolled in the study, all the screening procedures will be documented in the screening logs and appropriate case report forms (CRFs) will be completed before starting the procedures specific to the control or intervention arm, including:

- a) Basic socio-demographic information
- b) Relevant medical history
- c) Physical exam

Basic sociodemographic information and relevant medical history will be collected from the

This project is part of the EDCTP2 programme supported by the European Union

participant/caregiver or, if available, from existing medical records. A locator form (as a source document) will include contact information of the participant and/or caregiver or relative (with at least one mobile phone number to reach out the participant after discharge).

Time from admission (as recorded in medical history) to study enrolment will be recorded. However, this time should be as short as possible, preferably less than 12-24 hours.

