13.2.2 Statistical methods

Variables will be summarized using descriptive statistical methods. Continuous data will be described using the mean and standard deviation statistics when these values follow the normal distribution. Otherwise we will use the median and interquartile range when we will not assume this distribution. Categorical values will be summarized using frequency and/or percentages.

For categorical comparisons we will use a Chi-square test or Fisher exact test according to the

This project is part of the EDCTP2 programme supported by the European Union

data characteristics. Likewise, the continuous comparisons will be tested by Student t-test, Anova test or Kruskal Wallis test.

When necessary, we will transform the continuous data, especially laboratory data, in non-linear scale. For these cases we will describe these data with geometric mean. Heterogeneity between sites will be analyzed.

Assessment of loss to follow-up as random across arms

We will analyze the baseline characteristics between lost and non-lost follow up patients and across arms to ensure that loss to follow up occurs randomly. If we find any significant attribute we will adjust the analysis by this/these factors.

Time-to-event data

Time-to-event data (such as time to mortality, time to TB diagnosis or time to treatment initiation (among lab confirmed or all TB)) will be presented using Kaplan-Meier curves with a log rank test (two-sided 0.05 significance level). The analysis of covariates on time-to-event data will be performed using a Hazard Ratios estimated through Cox regression models.

Comparisons between control and intervention arm will be established at prespecified time points (day 7, day 14, day 28 and day 56). Mean time (and SD) to event per study arm will also be estimated.

Significance levels

The significance level for most comparisons is $p=0.05$. For selected secondary endpoints measured at several timepoints and subgroup analysis, the significance level will be $p=0.01$

Study discontinuations & patient disposition

Patient disposition and reasons for premature discontinuations and their frequencies will be tabulated.

Datasets analyzed

Number of patients in each analysis set will be tabulated and listings of any patients excluded from any analysis set will be provided.

Efficacy analysis

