### Exclusion criteria:

1. Unable to provide informed consent (if no authorized relatives are in the position to provide the consent).
2. Living outside the catchment area of the participating hospital(s).
3. With plans to migrate outside the catchment area within 2 months after recruitment.
4. Currently receiving anti-TB therapy or having received anti-TB therapy in the last 6 months prior to enrolment.
5. Receiving preventive TB treatment in the preceding 6 months
6. Participants admitted for traumatic reasons, acute abdomen, delivery or pregnancy (maternal conditions), or for planned/scheduled surgery.
7. Referred from other hospital
8. Positive result to a SARS-CoV-2 test (RT-PCR, antigen test, or other similar test that might define COVID-19 case in the study site)\*

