#### 4.4 Study Variables

The Baseline participants variables we will collected from TB-CAPT-HIV EXULTANT-BaselineCharacteristics-v3, and the following versions of this document. From this CRF the important variables for the analysis are:

Variable		Used in
Label	name	
Date of enrolment	ENROL_D	To calculate endpoints related to time.
Time of enrolment	ENROL_T	To calculate endpoints related to time.
Country	COUNTRY	To adjust some regression models.  For previous analysis about at random lost to follow up.
Sex	SEX	To describe the participant's profile.  For previous analysis about at random lost to follow up.
Ethnic group	ETHNIC ETHNIC_SPEC	To describe the participant's profile.  For previous analysis about at random lost to follow up.

Level of education	EDUCATION EDUCATION_SPEC	To describe the participant's profile.  For previous analysis about at random lost to follow up.
Employment Status	EMPLOYMENT EMPLOYMENT_SPEC	To describe the participant's profile.  For previous analysis about at random lost to follow up.
Type of Employment:  2.6 Is the patient employed as a health care worker?  2.7 Is the patient employed as a prison warder/work at a correctional facility?  2.8 Is the patient employed as a miner?	EMPL_HLTH_YN  EMPL_PRSN_YN  EMPL_MINE_YN	To describe the participant's profile.  For previous analysis about at random lost to follow up.
Early HIV positive result  3.1.1 Date of earliest HIV positive result:	HIV_POS_DATE	To describe the participant's profile.  For previous analysis about at random lost to follow up.
Current taking antiretroviral	ART_YN	To describe the participant's profile.  For previous analysis about at random lost to follow up.
Previous TB episodes	TB_TX_YN	To describe the participant's profile.  For previous analysis about at random lost to follow up.
Received BCG vaccination	BCG_YN	To describe the participant's profile.  For previous analysis about at random lost to follow up.

Participant live alone?		To describe the participant's profile.  For previous analysis about at random lost to follow up.
Patient taking cotrimoxazole?	CTX_YN	To describe the participant's profile.  For previous analysis about at random lost to follow up.
High blood pressure	HIGH_RR_YN	To describe the participant's profile.
Diabetes	DIABETES_YN	To describe the participant's profile.
Cardiac disease	CARDIAC_YN	To describe the participant's profile.
Epilepsy	EPILEPSY_YN	To describe the participant's profile.

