### 6.3 Multiple Testing

We consider unnecessary to apply a general adjustment of significance level by multiple comparisons test. We will use the all the statistical power for inference only in the primary study objective. To evaluate the other study endpoints, we use the p-value threshold at 0.05 to find the differences in our study without the objective to extrapolate the results to the global community. However, we will establish a p-value of 0.01 as a threshold for statistical significance in the comparisons related to a) selected secondary efficacy analyses (section 8.2, analyses 8.2.5, 8.2.6, 8.2.7) and subgroup analysis (see section 9.0)

We will adjust the results by site, demographic variables, and other baseline variables if we will detect differences or if these variables have a confounder characteristics profile. To decide this, we will do a preliminary analysis of these variables between sites.

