## 10. Other Analyses

We will do a comparison of baseline characteristics between participants who can complete the study and participants who we will lose during their follow-up period. We will do this analysis to test if the participant loss is by chance. We will use Chi statistical test. The variables that we will test are: Country (COUNTRY), Sex (SEX), Ethnic group (ETHNIC), Level of education (EDUCATION), Employment Status (EMPLOYMENT), Early HIV positive result (EARLY\_HIV), Current taking antiretroviral (ART\_YN), Previous TB episodes (TB\_TX\_YN), Received BCG vaccination (BCG\_YN), Participant live alone? (ALONE), Patient taking cotrimoxazole (CTX\_YN), Karnofsky Performance Status Scale (KARNOFSKY), Patient's WHO clinical Stage (WHO\_STAGES) and TB treatment start (TB\_TX\_START\_YN).

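### TB treatment start is listed as a baseline characteristic in the loss-to-follow-up comparison and can trigger adjustment, although in eligible participants it is either constant or recorded after enrolment

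*Protocol*

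**What the plan says.** **Eligibility.** Protocol exclusion criterion 4 (synopsis and 9.2.3) removes anyone "Currently receiving anti-TB therapy or having received anti-TB therapy (or a TB diagnosis) in the last 6 months prior to enrolment". The SAP's version omits the diagnosis clause but keeps the treatment bar: "Currently receiving anti-TB therapy or having received anti-TB therapy in the last 6 months prior to enrolment".

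**Baseline list.** SAP 4.4 opens its first table with "The Baseline participants variables we will collected from TB-CAPT-HIV EXULTANT-BaselineCharacteristics-v3". TB treatment start (TB_TX_START_YN) is a row in that table, to be used for the participant profile and for the analysis of random loss to follow-up. Previous TB episodes are a separate row (TB_TX_YN). The same table also holds the allocated arm and the randomisation date. Neither document defines TB_TX_START_YN or gives it a time window.

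**Loss comparison.** SAP 10 plans a "comparison of baseline characteristics between participants who can complete the study and participants who we will lose during their follow-up period", by chi-square. Its list of variables ends "and TB treatment start".

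**Adjustment.** Under its heading on random loss to follow-up, protocol 13.2.2 says: "If we find any significant attribute we will adjust the analysis by this/these factors". SAP 6.3 has a broader rule: "We will adjust the results by site, demographic variables, and other baseline variables if we will detect differences".

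**Endpoint.** The primary endpoint counts participants with confirmed TB who start treatment within 72 hours of enrolment, over all enrolled (protocol 8.1, SAP 3.4.1). SAP 4.4 builds it from the HOSP_TB_TX fields of the Hospitalization form.

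**The concern.** A covariate in a randomised comparison should be fixed before allocation. Under exclusion 4, no correctly enrolled participant is on TB treatment at enrolment. A column of uniform 'No' cannot be tested, so listing the item for a chi-square test presumes that it varies. In eligible participants the main source of variation would be treatment begun after enrolment. The strategy under trial is meant to bring that about, and it is one of the two conditions in the primary endpoint.

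If the loss test on the item were significant, the protocol's rule would put a consequence of allocation into the arm comparison as a covariate. Part or all of the effect that runs through treatment would then be removed. Eight-week mortality is exposed in the same way, because earlier treatment is the route by which the strategy is expected to save lives.

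**Working it through.** **1. The plan's own figures.** SAP 5 assumes 19% v 26%, two-sided alpha 0.05, 80% power and 5% loss. With the pooled normal formula:

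n = [1.96·√(2·0.225·0.775) + 0.8416·√(0.19·0.81 + 0.26·0.74)]² / 0.07² ≈ 557.5, so 558 per arm.

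558 × 1.05 = 586, the stated size (558/0.95 would give 588). The 7-point difference is therefore the right benchmark.

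**2. What the item can record in an eligible participant.**

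- Treatment at or shortly before enrolment: barred by exclusion 4, so a 'Yes' is an eligibility deviation.
- An older episode: already covered by TB_TX_YN.
- Nothing: always 'No', so there is nothing to test or adjust for.
- A start after enrolment: affected by allocation.

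The loss rule needs variation to fire. Apart from deviations, that variation comes mainly from the last case.

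**3. Effect of adjusting, if the item captures every start within 72 hours.** Let u be the share per arm treated without confirmation (an assumption). Treated shares are tc = 0.19 + u and ti = 0.26 + u. Success is possible only among the treated, so the Mantel-Haenszel risk difference is

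RD = w1·(0.26/ti − 0.19/tc) / (w1 + w0), with w1 = tc·ti/(tc + ti) and w0 = (1−tc)(1−ti)/(2−tc−ti).

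For u = 5%: tc = 0.24 and ti = 0.31. The difference among the treated is 0.8387 − 0.7917 = 0.0470. The weights are w1 = 0.1353 and w0 = 0.3617, so RD = 0.2722 × 0.0470 = 0.0128.

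| u | tc | ti | Adjusted difference (points) | Share of 7.0 removed |
|---|---|---|---|---|
| 0% | 19% | 26% | 0.0 | 100% |
| 5% | 24% | 31% | 1.28 | 82% |
| 10% | 29% | 36% | 2.17 | 69% |
| 15% | 34% | 41% | 2.81 | 60% |
| 20% | 39% | 46% | 3.31 | 53% |

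**4. Relaxing the assumptions.**

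- *Substitution for empirical treatment.* If half of the extra confirmed cases would have been treated anyway, ti falls by 3.5 points. The adjusted difference is then 3.95 (u = 5%), 4.45 (u = 10%) or 5.07 (u = 20%) points, that is 44%, 36% or 28% removed. If all would have been treated anyway (u of 10% or more), the treated shares are equal and 7.0 points remain.
- *Partial capture.* If the item records only a fraction f of starts, for example same-day starts, then with u = 10% and no substitution the adjusted difference is 6.12, 5.06 or 3.77 points for f = 25%, 50% or 75%. That is 13%, 28% or 46% removed.
- *Fixed before randomisation.* A value balanced by allocation leaves 7.0 points.

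**5. Could the trigger fire?** Take 1172 participants, 27.5% treated (the mean of 24% and 31%) and about 5% loss overall. Loss of 2% in treated v 6.1% in untreated gives a significant chi-square in about 89% of simulated trials, and 3% v 5.8% in about 50%. These loss rates are illustrative; the documents give none by treatment status.

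**The case against.** The strongest reply is that an undefined form field is being read as an outcome.

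- **Timing.** Protocol 10.4 says the enrolment forms "will be completed before starting the procedures specific to the control or intervention arm", and 10.8 puts baseline information before randomisation. That the form also holds the allocated arm shows only that some fields are filled after allocation.
- **Other sources of a 'Yes'.** An eligibility deviation, or a start in any gap between the eligibility check and allocation, would also count. A start without confirmation is not an endpoint success. The endpoint itself uses the HOSP_TB_TX fields.
- **The adjustment chain spans two documents.** SAP 10 only tests whether loss is by chance. The significant-attribute rule is in the protocol, which does not name this variable or say that the rule covers the primary comparison. SAP 8.1 specifies an unadjusted z-test, and SAP 6.3 rests its decision on a preliminary analysis between sites. Protocol 13.2.1 ties losses and deaths to specific secondary endpoints, although the synopsis applies the 5% loss to the primary endpoint.

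These points stand as limits. A reader might infer that all variation in the item belongs to the primary outcome, or that the SAP commits the primary analysis to this adjustment. The text supports neither.

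They do not rescue the listing. If the form is closed before allocation, the item is constant in eligible participants and the test is empty. If it is not, the item is a post-randomisation variable, and deriving the endpoint from other fields does not make it a safe covariate. A deviation should be listed as such, not adjusted for.

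**Conclusion.** The point holds in a conditional form. The SAP treats TB treatment start as a baseline characteristic in the loss comparison, and the protocol's rule can carry it into an arm comparison. Eligibility deviations aside, the item is either uninformative or recorded after enrolment and affected by allocation.

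The harm depends on what the item captures. It would be tempting to conclude that adjustment removes most of the effect, but the range runs from none to all of the assumed 7 points. The falls to 1.3 and 2.2 points need three things at once: capture of every 72-hour start, 5% or 10% per arm treated without confirmation, and no substitution for empirical treatment. All three are assumptions. For eight-week mortality the exposure is the same in kind, but the documents do not allow it to be sized.

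The change is worth making because the listing serves no purpose on either main reading and can do harm on one.

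**What to change.** - Remove TB_TX_START_YN from the baseline and loss-analysis uses in SAP 4.4 and from the test list in SAP 10. Keep it only as an eligibility check against exclusion 4, with its definition and time window stated.
- State in SAP 6.3 and 10 and in protocol 13.2.2 that only variables fixed before randomisation may be used as adjustment covariates in arm comparisons.
- Allow post-randomisation variables, including treatment start, to be described by loss status when missing-data mechanisms are studied under SAP 6.2. Describing them is legitimate; adjusting the arm comparison for them is the problem.

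The cost is a wording change in the two documents. It needs no new data, no participants and no change to the sample size.

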5.1 Background and statement of the problem

Tuberculosis (TB) is a leading cause of death worldwide and ranks above HIV/AIDS as the leading cause of mortality from a single infectious agent^{1,2}. The World Health Organization (WHO) estimated that there were around 10 million new cases and 1.5 million deaths in 2018.² Nine and 17% of the total number of TB cases and deaths respectively occurred in people living with HIV (PLHIV), with 70% of these occurring in the African region.² PLHIV are at increased risk of acquiring *Mycobacterium tuberculosis* (*Mtb*) infection and have a >20-fold increased risk of TB disease progression compared to HIV-uninfected peers.³⁻⁵ In addition, mortality during TB treatment remains as high as 11% globally, although fatal outcomes of PLHIV under TB treatment are even higher in Sub-Saharan African countries.²

One of the main barriers for ensuring timely TB treatment in PLHIV is the lack of an optimal diagnostic work up.⁶ In fact, TB case detection among people with HIV remains disappointingly low and almost half (45%) of all HIV associated TB cases are estimated to be undiagnosed or unreported.² Mortality associated with undiagnosed TB among people with HIV is assumed to be higher than 70%.⁷ Although the lack of a proper diagnosis is a multifactorial problem associated with quality of health care, social, economic and anthropological factors, the unavailability of rapid, sensitive and cheap diagnostic tools has been deemed as an important factor contributing to under- and misdiagnosis. In addition, poor awareness of TB by health care workers and lack of established diagnostic algorithms further hinder adequate TB diagnosis in many high burden settings.^{8,9} Autopsy studies conducted in sub-Saharan Africa show high rates of clinico-pathological discrepancies and missed TB which lead to high mortality^{8,10-12}

Among PLHIV, microbiological confirmation of TB is suboptimal due to sputum collection challenges and paucibacillary sputum resulting in poor diagnostic yield.¹³⁻¹⁵ Despite increasing availability, sputum Xpert® MTB/RIF (Cepheid Inc., Sunnyvale, CA, USA, hereinafter Xpert) confirms TB in only 77% of adult cases with HIV-infection¹⁶ and only 66% of culture-positive pediatric cases.¹⁷ Sensitivity of the next-generation Xpert MTB/RIF Ultra (hereinafter Ultra) is estimated to increase among adult TB patients with documented HIV-infection (90%)¹⁶. Yet, performance in immunosuppressed HIV positive patients (in whom sample collection is often unavailable) is probably suboptimal. Thus, estimates of Xpert diagnostic performance in general HIV positive patients may not reflect test performance within the majority of TB cases in hospitalized PLHIV. In addition, although Xpert results could, in theory, be available within a few hours, results are often available within several days after sample collection,^{18,19} delaying TB treatment if not empirically

This project is part of the EDCTP2 programme supported by the European Union

provided. The most sensitive test for TB diagnosis, liquid culture, is further handicapped as it is slow, expensive and contaminated 5-8% of the times.²⁰

Options that have been recommended by WHO to ensure earlier diagnosis and reduce mortality include strategic placement of rapid molecular TB diagnostics such as Xpert²¹ or Ultra²² within HIV care settings (which could enable availability of results within 24 hours), and uptake of the lateral flow urine lipoarabinomannan assay (LF-LAM)²³ strip-test – the Alere Determine™ TB LAM Ag (AlereLAM) for seriously ill PLHIV. However, despite AlereLAM being a cheap and fast test, only 9 of the 30 high TB and HIV burden countries have a national policy and algorithm indicating the routine use of urine LF-LAM (with various levels of implementation).² A recent study showed that urine-based TB screening of PLHIV admitted to hospital might reduce 56-day mortality in those with low CD4 counts, severe anaemia or clinically suspected tuberculosis.²⁴ A recently published meta-analysis showed that, as a screening test among PLHIV, AlereLAM has limited sensitivity of 45% (95% CI: 29-63) and specificity of 92% (80-97) against a composite microbiological reference standard.²⁵ However, screening with AlereLAM improves the likelihood of being diagnosed with TB during admission. The WHO recently expanded the recommendations for the use of AlereLAM to include adults, adolescents and children living with HIV with signs and symptoms of TB (inpatient and outpatient setting) or irrespective of signs and symptoms of TB with CD4 cell count under 200 cells/mm³ in inpatient settings irrespective of the CD4 cell count in outpatient settings.²⁶ The unavailability of CD4 counts upon admission or the assessment of the criteria for severely-ill or advanced HIV disease might delay quick testing of PLHIV in whom AlereLAM is recommended. In addition, LAM tests do not provide any information on potential resistance to anti TB drugs, which might hinder its implementation in high TB drug resistance settings.

The limitations of existing sputum-based tests for *M. tuberculosis* (*Mtb*) diagnosis create imperatives to explore the usefulness of easy to collect, non-respiratory specimens which could improve performance of all tests, while supporting treatment guidance and monitoring. In fact, the WHO has specified the need for rapid non-sputum based TB diagnostics among their high priority target product profiles for new TB diagnostics.²⁷

